Physical Activity and Pacemaker Study NCT03052829 Initial Protocol approved: 12/21/2016 Phy

Overview of approach: Based upon our previous work, the overall experimental design of this study is a small pragmatic randomized controlled trial (RCT). A general study diagram of events and procedures is present in Figure 2. Potential subjects who fit inclusion/exclusion criteria will be approached for enrollment once they are identified as candidates for permanent pacemaker implantation or as patients with already implanted Medtronic Revo or EnRhythm pacemakers. Individuals with, on average, less than 2 hours/day of active minutes over the prior 3 months (based in the pacemaker's internal accelerometer daily active minute reading) will be eligible for randomization. For individuals enrolled at the time of pacemaker implantation, the average active minutes for the time period of 3-6 months following implantation will be used to assess eligibility for randomization. At the time of enrollment all subjects will have a detailed medical history obtained. Thirty participants will be randomized across 2 parallel groups: an intervention group (n=15), or a Patient Usual Care (PUC) group (n=15). The PAC intervention follows the 5 A's (Assess, Advise, Agree, Assist, Arrange) model, which has been shown to be an effective clinical counseling tool for other health behaviors.14 Implanted Medtronic Pacemaker accelerometer data will be used to Assess physical activity levels. Subjects in the low active group will be referred to an intervention expert on the study staff. Eligible patients will then be Advised of their activity levels, and migrate through the 5 A's intervention model for 12 weeks. A fuller description of the intervention is included below. At the end of the 12 week active intervention, subjects in the intervention arm will enter a maintenance phase for an additional 3 months. During the study, pacemakers will be interrogated remotely or at clinic visits every 3 months. All subjects in the intervention arm will be contacted every 2 weeks to assess how they are doing with respect to the intervention. The study schema is shown in Figure 1, described in accordance with the CONSORT statement's recommendations for randomized clinical trials. An outline of study procedures is presented in Table 1.

Study setting.

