Subjects will be recruited from individuals who require permanent pacemaker placement at Froedtert Hospital and Zablocki VA Medical Center, both located in Milwaukee, WI.

Participant eligibility and recruitment.

Criteria for Enrollment and Randomization.

Inclusion Criteria:

1) Age \geq 55 years old

2) Clinical indication for placement of permanent pacemaker or currently implanted pacemaker

3) LVEF of \geq 50% by most recent echocardiogram.

4) Able to ambulate

5) Average active time of ≤ 2 hours/day based on Revo or EnRhythm Accelerometer read out for the 3 month period prior to enrollment

6) Able to take 650 steps over 10 minutes following pacemaker implantation (~2-2.5 mph walking speed)

Exclusion Criteria:

1) Follow up for implantation planned at a non-study center at the time of implantation.

2) Individuals with and expected life span of 1 year or less at the time of implantation

3) Known history of cognitive impairment or inability to follow study procedures

4) Lack of stable internet access

Randomization. Randomization will occur at the patient level. Upon potential eligibility being identified, subjects will be randomized in 3 blocks of 10 participants and randomized 1:1 to each study arm. We will enroll until we reach 15 subjects in each study arm who complete all study procedures. Randomization will be delivered via a random number generation sequence. Due to the nature of the trial, research staff, clinicians, and patients will not be blinded to patient assignment.

Physical Activity Counseling Intervention Group: The 12 week intervention is a multifaceted intervention that follows the 5 A's (Assess, Advise, Agree, Assist, Arrange) model, designed to be both simple to implement and follow for patients. It mimics a referral for education model that is used for patients who require a nutritionist or other specialist for behavioral modification. The intervention includes the following elements.

1) Assess: Subjects will undergo a physical activity assessment, utilizing the implanted Medtronic Pacemaker accelerometer data.

2) Advise: Eligible patients will be shown the graph from our recent publication demonstrating the relationship between decreased active minute time and mortality to help build the case that an intervention is necessary.

3) Agree: Those patients who agree enter into a shared decision making process to behavior change – in this case modifying physical activity behavior in an effort to decrease sedentary time.

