4) Assist: The patient will receive a written prescription that includes their baseline Medtronic Pacemaker accelerometer data, and a target to increase their activity. Activity will be increased using the following:

a. Self-regulatory monitoring: A pedometer with a target to increase steps by 10% per week, to a target of 10,000 steps/day. A calendar will be given for patients to write down daily amounts.

b. Brief printed support materials – on different behavioral strategies to increase active behaviors

c. A list of freely available internet-resources

d. Bi-weekly telephone support: A member of the study staff will call each participant randomized to the PAC intervention group every other week. Calls will be limited to 5 minutes and used to offer support, advice, and solicit feedback.

5) Arrange: A follow-up visit will be arranged for week 12, to retrieve outcome data for physical activity from the implanted Medtronic Pacemaker accelerometer. Alternatively, data will be obtained through convenient methods.

Overall, our approach employs key strategies proven to increase the adoption and retention of lifestyle integrated habitual physical activity in older adults.15,16 These strategies included the use of frequent feedback,15 selfregulation of activity,17,18 education and practice in realistic behavioral change strategies and goal setting,16 and rewarding.19

Patient Usual Care (PAC) Group: The PAC group will undergo Implanted Medtronic Pacemaker Accelerometer data retrieval, but this data will not be shown to the patient, nor used to alter behavior. This group will follow their typical clinical routine, and therefore represent a usual care approach.

Communication of Physical Activity information: All individuals with pacemakers will undergo interrogation of their device every 3 months during entire study period, including intervention phase and follow-up phase.

Outcomes: The primary outcome for this study is the number of active minutes as measured by the Medtronics Implanted Pacemaker accelerometer.

Statistical Methods: Baseline demographic and clinical data will be compared between groups by unpaired t-tests, Chi-squared tests, or non-parametric equivalents as appropriate. The primary outcome will be compared between

Data Analyses

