SPSS 24 and SigmaStat 12.5 were employed for data analyses. Data will be analyzed on a per protocol basis given that the goal of this pilot. Baseline characteristics will be compared between groups using unpaired t-tests, chi-

square, or Fisher's Exact test as. Differences in step counts and pedometer determine active time over the study period will be investigated using general linear models for repeated measures with the randomization group assignment as the between subjects variable and a three factor within subjects comparisons representing the three measurement time points with the Tukey test applied for post-hoc comparisons if significance of the overall models was detected. Correlations between step count measurements and PDAH measurements were performed using Pearson's r test. *P* < 0.05 were considered significant.

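### The plan sets no rule for repeated visits in its Pearson correlation of step count with PDAH; pooling visits as independent would understate the uncertainty (minor)

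*Combined protocol and SAP*

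**What the plan says.** The correlation is described in one sentence of the Data Analyses section: "Correlations between step count measurements and PDAH measurements were performed using Pearson's r test". The 0.05 significance level follows directly. No visit, averaging rule or allowance for repeated pairs is given.

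The sentence before it covers step counts and pedometer active time. These "will be investigated using general linear models for repeated measures with the randomization group assignment as the between subjects variable", with "a three factor within subjects comparisons representing the three measurement time points". The plan therefore treats step counts as repeated within patients when it compares the arms.

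On the device side, the section on communication of physical activity information says: "All individuals with pacemakers will undergo interrogation of their device every 3 months during entire study period". The Overview of approach adds that, after the 12-week intervention, "subjects in the intervention arm will enter a maintenance phase for an additional 3 months". Together these suggest device readings at about baseline, 3 months and 6 months. The abbreviation PDAH is not expanded anywhere in the supplied text, so three PDAH readings per patient is an inference.

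On numbers, the Overview plans thirty patients in two arms of 15, and the Randomization paragraph says: "We will enroll until we reach 15 subjects in each study arm who complete all study procedures".

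**The concern.** The plan recognises within-patient repetition for the arm comparison. It then names, for the correlation, a test whose p-value and interval assume that each pair is independent of the others. An active patient tends to be active at every visit on both measures, so three pairs from one patient carry less information than three pairs from three patients. If all pairs enter one Pearson test, the nominal sample size is too large, the p-value too small and the interval too narrow.

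A single coefficient over all visits and both arms also mixes three things: differences between patients, changes within a patient, and any shift that counselling produces in both measures. What is at stake is how the association between step count and the device measure is read. The primary outcome comparison is not affected.

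**Working it through.** The plan gives no sample size, power or precision figure for the correlation, so there is no figure to reproduce. The check asks what happens if visits are pooled.

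**Inputs from the document**
- 30 patients, 15 per arm (Overview of approach; Randomization).
- k = 3 time points, stated for the pedometer measures (Data Analyses) and inferred for PDAH. This gives 30 × 3 = 90 pairs.
- Alpha 0.05; sidedness is not stated.

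**Assumptions**
- Two-sided test.
- No true association.
- Equal correlation between any two visits of a patient, with the same ICC for both measures. The document gives no ICC, so a range is shown.

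**Formulas**
- Design effect D = 1 + (k − 1) × ICC_x × ICC_y = 1 + 2 × ICC². At ICC 0.5, D = 1 + 2 × 0.25 = 1.50.
- Effective number of pairs = 90 / D. At ICC 0.5 this is 90 / 1.50 = 60.
- Approximate type I error = 2 × [1 − Φ(1.96 / √D)].
- Interval widening under zero correlation = √D.

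**Results** (40,000 simulated trials per row)

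| ICC | D | Effective pairs | √D | Type I error, formula | Type I error, simulated |
|---|---|---|---|---|---|
| 0 | 1.00 | 90 | 1.00 | 5.0% | 5.1% |
| 0.3 | 1.18 | 76 | 1.09 | 7.1% | 7.2% |
| 0.5 | 1.50 | 60 | 1.22 | 11.0% | 10.8% |
| 0.7 | 1.98 | 45 | 1.41 | 16.4% | 16.6% |
| 0.8 | 2.28 | 39 | 1.51 | 19.4% | 20.0% |
| 0.9 | 2.62 | 34 | 1.62 | 22.6% | 24.0% |

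A separate simulation gave about 8% at ICC 0.3, hence the range 7–8%. If only 15 patients contribute (45 pairs), inflation is much the same: 7.2% at ICC 0.3 and 24.2% at 0.9.

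**Precision.** The critical |r| is 0.207 for 90 independent pairs and 0.361 for 30. At an observed r of 0.5, the Fisher-z 95% interval is 0.33 to 0.64 with 90 pairs and 0.17 to 0.73 with 30. The 30-pair interval is what one pair per patient would give.

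**Separate tests at each visit.** Each is valid for its own visit. The chance of at least one false positive is 1 − 0.95³ = 14.3% if the tests are independent. Because the same patients return, it is lower: 11.6% at ICC 0.8 and 9.8% at ICC 0.9.

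**Choice of replacement.** With no treatment effect, a repeated-measures correlation with patient as the only factor holds about 5%. If counselling shifts both measures in one arm after baseline, it does not. With no other association and ICC 0.8, it rejects in 26–27% of trials for a 0.5 SD shift and in 82% for a 0.8 SD shift. Adding visit and arm-by-visit terms, or adjusting patient means for arm, holds about 5%.

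**Degrees of freedom.** Within patients: 90 pairs − 30 patient terms − 2 visit terms − 2 arm-by-visit terms − 1 for the correlation = 55. Between patients: 30 − 2 arm means − 1 = 27.

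**The case against.** The strongest reply is that the plan does not contain the error. It nowhere says that visits are pooled, and the plural in its sentence fits a visit-by-visit analysis, where each Pearson test is valid. The authors used a repeated-measures model one sentence earlier, so they knew that the data were repeated. This stands: the defect is a missing specification, and a reader who infers that 90 pairs were certainly treated as independent goes beyond the text.

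Four further points stand in part.

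- Three PDAH readings are inferred. The pedometer is described only for the intervention arm, although the arm comparison of step counts implies that both arms have them.
- Zero true correlation is an unlikely null if PDAH is a device activity measure. The realistic harm is then overstated precision more than false discovery, and the √D widening is derived at zero correlation, so it is only a guide elsewhere.
- The inflation depends on an assumed ICC and vanishes if either measure has an ICC near zero.
- The multiplicity complaint against per-visit tests is weak. Two replacement correlations carry 1 − 0.95² = 9.75% if independent and both tested at 0.05.

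A reader might also take the correlation as the trial's evidence that step counts and the device agree. The document gives it no such purpose, and correlation measures association, which is not agreement.

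The reply does not remove the gap. The wording allows an invalid analysis, does not name a valid one, and leaves the choice of pairs open until the data are seen.

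**Conclusion.** The concern holds in conditional form. The plan names an ordinary Pearson test for measures that are, or probably are, repeated within patients, and gives no rule for the repeated pairs. If visits are pooled, the true type I error runs from about 7–8% (ICC 0.3) to 24% (ICC 0.9) against a nominal 5%, and the interval is too narrow. This rests on 30 patients × 3 visits, no true association and equal ICCs in the two measures. Separate per-visit tests avoid that fault but do not show whether the two measures move together within a patient.

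The priority is minor. This is a secondary analysis with no stated decision role, and the primary outcome, device-measured active minutes, is unaffected.

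**What to change.** Define PDAH, and replace the correlation sentence with:

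> Within-patient association between step count and PDAH will be estimated by a repeated-measures (partial) correlation from a linear model with patient, visit and arm-by-visit terms (55 df for 30 patients × 3 visits). Between-patient association will be estimated by the correlation of patient means adjusted for arm (27 df). Both will be reported with 95% confidence intervals; pairs from different visits will not be pooled as independent.

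If only the intervention arm has step counts, drop the arm terms and recompute: 45 − 15 − 2 − 1 = 27 df within patients and 15 − 2 = 13 df between patients, for 15 patients × 3 visits.

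The cost is a few lines of code and wider intervals than pooled pairs would give. If the correlation has already been run, as the past tense suggests, it can be redone on the existing data.
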